5.7 EVALUATIONS DURING TREATMENT

The following assessments will be done while the patient is on treatment ([Table 6](#)).

Table 6. Evaluations during treatment.

	ASSESSMENT	TIME
1. Clinical examination	♦ Complete physical examination, including weight and calculation of BSA.	Cycle 2 and beyond: Day 1 of each cycle (always prior to treatment infusion).*
	♦ Performance status (ECOG PS). ♦ Vital signs: heart rate, blood pressure and body temperature.	Day 1 of each cycle (always prior to treatment infusion).*
	♦ Concomitant therapies.	Throughout the “on treatment” period.**
2. Laboratory tests	♦ Hematology: differential WBC counts (including neutrophil, lymphocyte and monocyte counts), platelet count and hemoglobin. ♦ Biochemistry: Liver function test (ALT, AST, AP, GGT, total bilirubin; direct bilirubin only if total bilirubin is abnormally high); total proteins, albumin, creatinine, CPK, glucose, calculated CrCL (as per Cockcroft and Gault’s formula), and serum electrolytes (Na^+ , K^+ , Cl^-).	Cycle 1: Day 8.* Cycle 2: Day 1 (always prior to treatment infusion) and Day 8.* Cycle 3 and beyond: Day 1 of each cycle (always prior to treatment infusion). * Any patient presenting grade 4 treatment-related AEs should have any relevant tests re-assessed at least within 72 hours until recovery to at least grade 3.
3. Pregnancy test (if women of childbearing potential)	Assessment of β -hCG (urine or serum).	Repeat if applicable.
4. ECG	Cardiac rhythm will be identified in ECG intervals of at least 30 seconds of duration, PR interval, QT interval (raw), heart rate and QRS complex.	Repeat if clinically indicated.
5. LVEF	ECHO or MUGA.	Repeat if clinically indicated. In patients treated with PLD (Arm B), to be repeated every four cycles (or more frequently, if clinically indicated). After exceeding a cumulative anthracycline dose of 450 mg/m^2 , LVEF will be assessed before each PLD infusion.
6. Pharmacokinetics (in the PM01183 treatment arm only)	-	A total of eight blood samples (before PM01183 treatment start, 5 min before the end of PM01183 infusion, and 1 hour and 168 hours after the end of PM01183 infusion) will be collected for pharmacokinetic PM01183 analyses in Cycle 1 (four samples) and in a second cycle (between Cycle 2 and 4) (four samples) in patients treated in Arm A. The second cycle with blood sample collection for PK will be assigned once the patient is randomized into Arm A (see details in Section 7.7.1).

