6.3 STARTING DOSES AND SCHEDULE

6.3.1.1 Experimental Arm (PM01183): Arm A

- 3.2 mg/m^2 on Day 1 q3wk (three weeks = one treatment cycle)

Dose will be rounded to the first decimal.

6.3.1.2 *Control Arm (PLD and topotecan): Arm B*

- **PLD starting dose and schedule:**

50 mg/m² on Day 1 q4wk (four weeks = one treatment cycle).

Dose will be rounded to the first decimal.

Patients previously treated with PLD will be assigned to receive topotecan if they are randomized to the control arm.

- **Topotecan starting dose and schedule:**

- 1.50 mg/m² daily on Days 1-5 q3wk (three weeks = one treatment cycle) for patients with calculated CrCL \geq 60 ml/min.
- 1.25 mg/m² daily on Days 1-5 q3wk for patients with calculated CrCL between 40 and 59 ml/min.
- 0.75 mg/m² daily on Days 1-5 q3wk for patients with calculated CrCL between 30 and 39 ml/min.

Dose will be rounded to the first decimal.

Skipped doses of topotecan will not be replaced.

Patients previously treated with topotecan will be assigned to receive PLD if they are randomized to the control arm.

However, if the number of patients randomized to either PLD or topotecan reaches 60% of the total number of patients expected in the control arm (i.e. 126 patients), then the treatment of choice in the control arm will be restricted to the less frequent control drug until the end of accrual (see Section [5.6](#)).

The dose for all three agents (PM01183, PLD or topotecan) will be capped at a body surface area (BSA) of 2.0 m² in those patients who have a greater BSA. BSA will be calculated according to the standard nomogram used at each center.

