7.4 ADVERSE EVENTS REPORTING PROCEDURES

7.4.1 Reporting Adverse Events

The Sponsor will collect AEs until 30 days after administration of the last dose of study drug(s)/IMP(s) or until the start of a new antitumor therapy or until the date of death, whichever occurs first. All AEs suspected to be related to the study drug/IMP must be

followed-up after the time of therapy discontinuation until the event or its sequelae resolve or stabilize at an acceptable level to the Investigator and the Sponsor.

All AEs, including medication errors and uses outside what is foreseen in the protocol, must be recorded in English using medical terminology in the source document and the CRF. Whenever possible, the Investigator will record the main diagnosis instead of the signs and symptoms normally included in the diagnoses.

Investigators must assess severity (grade) of the event following the NCI-CTCAE v. 4 and assign a relationship to each study drug(s)/IMP(s); and pursue and obtain information adequate both to determine the outcome and to assess whether it meets the criteria for classification as a SAE requiring immediate notification to Pharma Mar S.A. or its designated representative. The Investigator must provide any relevant information as requested by the Sponsor in addition to that on the CRF.

Abnormal laboratory tests occurring during the study should only be recorded in the AE section of the CRF if the disorder:

- Is associated with clinically significant symptoms, and/or
- Leads to a change in study dosing or discontinuation from the study, significant additional concomitant drug treatment or other therapy, and/or
- Leads to any of the outcomes included in the definition of a SAE.

Otherwise laboratory results should be reported in the corresponding section of the CRF (e.g. biochemistry, hematology).

All episodes of febrile neutropenia must always be reported within 24 hours following the same procedure for reporting SAEs (see Section [7.4.2](#)), including episodes that occurred in patients without seriousness criteria. For these cases, the seriousness criterion should be reported as a medically significant event.

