8.3 Treatment Administration

Total cumulative dose, time on treatment, dose intensity and relative dose intensity, administration delay, and dose reductions/omissions will be described following standard tables (detailed in Appendix I) and the reported cycle information on the case report form (CRF) pages will be used for the analyses.

Total cumulative dose by drug, expressed in mg, is the sum of all the product doses from the first cycle until the last cycle, including the dose received in the last cycle.

Time on treatment, expressed in weeks, is defined as last infusion date minus first infusion date plus 30 days, except if the patient dies or starts a new antitumor therapy within 30 days from the last infusion date, in which case the time on treatment will be the date of death or the date of the start of a new antitumor therapy minus the date of the first infusion.

Intended dose intensity is the planned dose per cycle divided by the planned number of weeks by cycle.

Absolute dose intensity is the actual cumulative dose divided by the number of weeks of treatment. As a convention, for this calculation, the duration of the last cycle will be the predefined cycle length (i.e., 21 days or 28 days in case of PLD). Relative dose intensity (%) is the ratio of absolute dose intensity divided by the intended dose intensity.

The items « Infusion delayed: yes/no» and « Dose reduced: yes/no» present on the drug

administration CRF page will be used to calculate delays and dose reductions, respectively. For cycles considered as delayed by the Investigator, the length of the delay will be calculated as:

Duration of cycle delay: Date of the current drug administration – Date of the previous drug administration – the predefined cycle length (i.e., 21 days if PM01183/topotecan or 28 days if PLD).

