12.2 Adverse Events (AEs)

12.2.1 Adverse Events

Treatment emergent AEs will be described irrespective of their relationship to the drug and as drug-related events stated as Related to Study Drug or Unknown. Safety will be described according to the NCI-CTCAE v4. AEs consisting of laboratory abnormalities (e.g., neutropenia) may be under-reported as AEs. Since these events are better evaluated using objective laboratory results, laboratory abnormalities will be discussed in Section 12.4.

The type of toxicity and worst grade or severity by cycle and by patient will be summarized according to System Organ Class (SOC) and Preferred Term (PT) as per the MedDRA dictionary. Subsequent grouping of similar or clinically related items might be appropriate at the time of the analysis. Tables will be organized by category of events using SOC and in descending frequencies (e.g. higher to lower).

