12.2.2 Display of Adverse Events

Table 12.2.2.1 Summary of adverse events

Category	PM01183	Control
	N (%)	N (%)
Number of patients with any AE		
Number of patients with any drug-related AE		
Number of patients with any grade 3/4 AE		
Number of patients with any grade 4 AE		
Number of patients with any grade 3/4 drug-related AE		
Number of patients with any grade 4 drug-related AE		
Number of patients with any SAE in DB		
Number of patients with any drug-related SAE in DB		

Category	PM01183	Control
	N (%)	N (%)
Number of patients with any grade 3/4 SAE in DB		
Number of patients with any grade 4 SAE in DB		
Number of patients with any grade 3/4 drug-related SAE in DB		
Number of patients with any grade 4 drug-related SAE in DB		
Number of patients with death associated with AEs		
Number of patients with death associated with drug-related AEs		
Number of patients with treatment discontinuations associated with AEs		
Number of patients with treatment discontinuations associated with drug-related AEs		
Number of patients with delays associated with AEs		
Number of patients with delays associated with drug-related AEs		
Number of patients with reductions associated with AEs		
Number of patients with reductions associated with drug-related AEs		

Table 12.2.2.2 Drug-related adverse events. Worst grade by patient

Table 12.2.2.3 Drug-related adverse events. Worst grade by cycle

Table 12.2.2.4 Adverse Events regardless of relationship. Worst grade by patient

Table 12.2.2.5 Adverse Events regardless of relationship. Worst grade by cycle

Category/MedDRA Code		Grade																			
		PM01183										Control									
		1		2		...		G≥1		G≥3		1		2		...		G≥1		G≥3	
		N	%	N	%	N	%	N	%	N	%	N	%	N	%	N	%	N	%		
Blood and lymphatic system disorders																					
	Anaemia NOS																				
	...																				
Cardiac disorders																					
	Arrhythmia NOS																				
	...																				
...																					

Listing 12.2.2.6 Drug-related grade 3/4 adverse events. Worst grade by cycle

Treatment arm*	Patient id.	Cycle	SOC Name	PTCode	Grade

*PM01183, PLD or Topotecan

Listing 12.2.2.7 Grade 3/4 adverse events regardless of relationship. Worst grade by cycle

Treatment arm*	Patient id.	Cycle	SOC Name	PTCode	Grade

*PM01183, PLD or Topotecan

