	No. of patients evaluated	Grade 3/4	%	No. of patients evaluated	Grade 3/4	%	No. of patients evaluated	Grade 3/4	%
PM01183									
Thrombocytopenia									
Neutropenia									
ALKP									
Bilirubin									
SGOT-AST									
SGPT-ALT									
CPK									
Nausea									
Vomiting									
Fatigue									
Other*									
Control									
Thrombocytopenia									
Neutropenia									
ALKP									
Bilirubin									
SGOT-AST									
SGPT-ALT									
CPK									
Nausea									
Vomiting									
Fatigue									
Other*									

*Any drug-related toxicity present in $\geq 3\%$ of cycles in any group.

Table 12.5.9 Worst grade by patient comparison vs. PLD

Laboratory abnormalities/ drug-related AEs	Grade																			
	PM01183										PLD									
	0		1		...		G≥1		G≥3		0		1		...		G≥1		G≥3	
	N	%	N	%	N	%	N	%	N	%	N	%	N	%	N	%	N	%	N	%
Thrombocytopenia																				
Neutropenia																				
ALKP																				
Bilirubin																				
SGOT-AST																				
SGPT-ALT																				
CPK																				
Nausea																				
Vomiting																				
Fatigue																				
Other*																				

*Any drug-related toxicity present in >=5% of patients in any group.

Table 12.5.10 Worst grade by cycle comparison vs. PLD

Laboratory abnormalities/ drug-related AEs	Grade																			
	PM01183										PLD									
	0		1		...		G≥1		G≥3		0		1		...		G≥1		G≥3	
	N	%	N	%	N	%	N	%	N	%	N	%	N	%	N	%	N	%	N	%
Thrombocytopenia																				
Neutropenia																				
ALKP																				
Bilirubin																				
SGOT-AST																				
SGPT-ALT																				
CPK																				
Nausea																				
Vomiting																				
Fatigue																				
Other*																				

*Any drug-related toxicity present in >=5% of patients in any group.

Table 12.5.11 Worst grade by patient comparison vs. topotecan

Laboratory abnormalities/ drug-related AEs	Grade																			
	PM01183										Topotecan									
	0		1		...		G≥1		G≥3		0		1		...		G≥1		G≥3	
	N	%	N	%	N	%	N	%	N	%	N	%	N	%	N	%	N	%	N	%
Thrombocytopenia																				
Neutropenia																				
ALKP																				
Bilirubin																				
SGOT-AST																				
SGPT-ALT																				
CPK																				
Nausea																				
Vomiting																				
Fatigue																				
Other*																				

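### By-cycle adverse event tables set 21-day PM01183 cycles against 28-day PLD cycles, so at equal weekly toxicity PLD can show up to about 1.3 times the PM01183 percentage

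*SAP*

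**What the plan says.** The protocol fixes different cycle lengths. PM01183 is given "on Day 1 q3wk (three weeks = one treatment cycle" (Protocol 6.3.1.1). PLD is given "on Day 1 q4wk (four weeks = one treatment cycle" (Protocol 6.3.1.2). Topotecan also has a three-week cycle. SAP 8.3 uses the same lengths in its delay formula, "the predefined cycle length (i.e., 21 days if PM01183/topotecan or 28 days if PLD", and allows for them in dose intensity.

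For adverse events, SAP 12.2.1 states: "The type of toxicity and worst grade or severity by cycle and by patient will be summarized according to System Organ Class". The shells follow from that:

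- SAP 12.2.2 has Table 12.2.2.3 (drug-related) and "Table 12.2.2.5 Adverse Events regardless of relationship. Worst grade by cycle", with N and % per grade under PM01183 and under a single Control heading.
- SAP 12.3.1 has the by-cycle serious event tables 12.3.1.2 and 12.3.1.4. Their columns are not visible in the available text, but SAP 7.4 says that serious events follow the adverse event layout.
- SAP 12.5 has "Table 12.5.10 Worst grade by cycle comparison vs. PLD", which sets PM01183 against PLD alone.

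By-patient versions stand beside these tables (12.2.2.2, 12.2.2.4, 12.5.9). Time on treatment is tabulated by drug in Table 12.1.1.1 but is not linked to adverse event counts. The collection window after the last dose is the same for every drug (Protocol 7.4.1): "The Sponsor will collect AEs until 30 days after administration of the last dose of study drug(s)/IMP(s", or sooner on new antitumor therapy or death.

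**The concern.** A percentage of cycles appears to adjust for how much treatment each arm received. It adjusts for the number of infusions, not for time under observation. Each PLD cycle is open for a further seven days in which an event can be recorded, so drugs with the same weekly toxicity will not show the same by-cycle percentage. The difference favours PM01183. Read the other way, equal by-cycle percentages under nominal windows would correspond to a weekly rate 28/21 = 1.33 times as high on PM01183.

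The pooled Control column adds a second difficulty. It mixes 21-day and 28-day cycles in proportions set by prior treatment, investigator preference and the 60% cap, so its by-cycle percentage depends partly on drug mix.

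The plan takes care over timing elsewhere. Tumor assessments are every eight weeks in both arms, and SAP 6.2 tests their symmetry. The adverse event comparisons have no counterpart, although the safety profile is a secondary endpoint of an open-label trial.

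**Working it through.** The plan gives no figure for this effect, so there is none to reproduce. The cycle lengths (21 and 28 days) and the 30-day tail come from the documents. The event rate per cycle, the numbers of cycles and the PLD share of control cycles are assumptions, shown over a range.

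**1. Nominal windows.** Assume a constant hazard, equal per week for both drugs. If a share p of 21-day cycles has an event, the share of 28-day cycles is 1 − (1 − p)^(28/21).

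| p, 21-day cycle | 28-day cycle | Ratio |
|---|---|---|
| 2% | 2.7% | 1.329 |
| 5% | 6.6% | 1.322 |
| 10% | 1 − 0.9^(4/3) = 13.1% | 1.311 |
| 20% | 25.7% | 1.287 |
| 40% | 49.4% | 1.235 |
| 85% | 92.0% | 1.083 |

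The limit for rare events is 28/21 = 1.333. For rates up to 20% the ratio is 1.29 to 1.33.

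**2. Last cycle counted to 30 days.** The SAP does not say how adverse events are assigned to cycles. If those in the 30 days after the last dose go to the last cycle, that cycle is equally long for every drug. The mean window over n cycles of length L is (L(n − 1) + 30)/n.

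- 5 PM01183 cycles: (21×4 + 30)/5 = 22.8 days. 4 PLD cycles: (28×3 + 30)/4 = 28.5 days.
- At p = 10%, a 30-day window gives 1 − 0.9^(30/21) = 13.97%. PM01183: (4×10% + 13.97%)/5 = 10.79%. PLD: (3×13.11% + 13.97%)/4 = 13.32%. The ratio is 1.234.
- At p = 2% and 20% the ratios are 1.247 and 1.217, so about 1.22 to 1.25.
- With 2 cycles each the ratio is 1.136 to 1.121 over the same rates. With 1 cycle each it is 1.00.

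**3. Pooled Control, nominal windows.** If PLD supplies a share s of control cycles, the ratio of Control to PM01183 is [s(1 − (1 − p)^(4/3)) + (1 − s)p]/p.

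- s = 40%: 1.132 at p = 2%, 1.115 at p = 20%.
- s = 60%: 1.197 at p = 2%, 1.172 at p = 20%.

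The 60% cap applies to patients, not cycles. At equal time on treatment, PLD patients contribute fewer cycles, so the PLD share of cycles would lie below its share of patients.

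**4. Rows affected.** Seven of the ten named rows in Table 12.5.10 are laboratory values, which SAP 12.5 takes from the laboratory forms. Scheduled sampling is per cycle, not per week. Cycle 1 has Day 8, Cycle 2 has Days 1 and 8, and then (Protocol 5.7): "Cycle 3 and beyond: Day 1 of each cycle (always prior to treatment infusion". A longer cycle adds no scheduled sample, so the window effect there is small or absent. That leaves nausea, vomiting, fatigue and the drug-related toxicities under Other. Every row of the 12.2.2 and 12.3.1 by-cycle tables is an adverse event row.

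**5. With a time denominator.** SAP 8.3 time on treatment ends on the same rule as adverse event collection. With patient-weeks as the denominator, an equal weekly rate gives a ratio of 1.00 whatever the cycle length.

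**The case against.** By-cycle reporting is a legitimate per-infusion measure. Re-treatment and dose reduction are decided cycle by cycle, and a clinician may want the chance of an event per administration. The tables are also lightly relied on: Table 12.5.10 has no p-value column, the Fisher tests (Tables 12.4.4.10 and 12.4.4.11) are by patient and exploratory, and by-patient tables are planned. All of this stands, and it is why the by-cycle percentage should be kept. It does not answer the point, because the shell is titled a comparison, carries no note on window length, and by-patient percentages are not rates per time either.

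The constant-hazard model can also be questioned. Emesis is likely to follow infusion closely, so days 22 to 28 would add little. A persisting event such as fatigue may be counted in every cycle whatever its length. Permitted delays of up to two weeks make actual windows differ from nominal ones. These objections limit the size; for events that do accrue over time, the direction remains.

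A reader might infer that PLD will look about 30% more toxic in every by-cycle table. The documents do not support that:

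- Table 12.5.12 compares PM01183 with topotecan, both on 21-day cycles.
- Tables 12.5.2, 12.5.4, 12.5.6 and 12.5.8 have age, race, prior lines or region as columns, with the arms as separate blocks. Their main contrast is within an arm.
- Only Table 12.5.10 isolates PLD. The other four tables use pooled Control, where the ratio is smaller.

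**Conclusion.** The point holds for adverse event rows in five tables: 12.5.10 against PLD, and 12.2.2.3, 12.2.2.5, 12.3.1.2 and 12.3.1.4 against pooled Control. The figure of 1.3 is near the top of a range, not an expected value. It needs a constant and equal weekly hazard, events in at most about 20% of 21-day cycles, and nominal windows or many cycles per patient. Each departure lowers it, as the working shows, and for patients with a single cycle counted to 30 days it vanishes.

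This is an interpretive bias in descriptive safety tables, in a known direction that favours PM01183. It does not touch the primary analysis, any error rate or any stopping decision. It is a worthwhile, inexpensive improvement, and it does not justify dropping by-cycle reporting.

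**What to change.** For the adverse event rows of Tables 12.5.10, 12.2.2.3, 12.2.2.5, 12.3.1.2 and 12.3.1.4:

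- Add episodes per 100 patient-weeks on treatment beside the by-cycle percentage, with time on treatment as defined in SAP 8.3.
- Label the by-cycle percentage *per infusion (21-day vs 28-day cycle)*.
- Replace the pooled Control by-cycle column with separate PLD and topotecan columns.

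A footnote should state how events after the last dose, and events that continue across cycles, are assigned to cycles. Table 12.5.12 and the laboratory rows can stay as they are.

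The cost is a few extra columns, shell wording and minor programming. Infusion dates and adverse event start and end dates are already in the planned listings, so no new data are needed.

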12.6 Concomitant Medication during Treatment

Table 12.6.1 Concomitant medication during treatment (ATC1/ATC2/ATC4)

Concomitant medication	PM01183		Control	
	N	%	N	%
Alimentary tract and metabolism				
Antiacids				
Magnesium compounds				
....				
Blood and blood forming organs				
Antithrombotic agents				
Vitamin K antagonists				
....				

Table 12.6.2 CSF, transfusions or EPO

	PM01183	Control					
		Total		PLD		Topotecan	
		N	%	N	%	N	%
CSF							
CSF (prophylactic)							
CSF (therapeutic)							
Platelets transfusions							
RBC transfusions							
EPO							

Listing 12.6.3 Patients who have been treated with CSF, transfusions or EPO

*PM01183, PLD or Topotecan

Table 12.6.4 Neutropenia by CSF, worst grade in the first cycle

12.7 Subsequent Therapy

Table 12.7.1 Subsequent therapy

	PM01183		Control					
			Total		PLD		Topotecan	
	N	%	N	%	N	%	N	%
Type								
Chemotherapy								
Surgery								
...								
Subsequent chemotherapy								
Platinum								
Taxanes								
...								

12.8 PRO at treatment

Completion rate is defined as the number of patients with answer to item X in the numerator and the number of patients on treatment in each time point as denominator.

Missing data will not be taken into account in the analyses; anyway, if the quantity is considered relevant then supportive analyses will be performed applying a conservative approach of assuming missing data as failures.

Table 12.8.1 Completion rate

Item	Cycle	PM01183		Control	
		Missing (%)	Completed (%)	Missing (%)	Completed (%)
EORTC QLQ-C30					
Item 1	Baseline				
	Week 6				
	...				
....	Baseline				
	...				
Any item	Baseline				
	Week 6				
	...				
EORTC QLQ-OV28					
Item 31	Baseline				
	Week 6				
	...				
....	Baseline				
	...				
Any item	Baseline				
	Week 6				
	...				
EORTC QLQ-C30 and QLQ-OV28					
Any item	Baseline				
	...				

Table 12.8.2 T-test change vs. baseline

Item	Cycle	PM01183		Control*		p-value
		N	Mean (std)	N	Mean (std)	
*Control refers to PLD and/or topotecan						
Item 1	Week 6					
	Week 12					
	...					
....	Week 6					
	Week 12					
	...					
Item 58	Week 6					
	Week 12					
	...					
*Control refers to PLD						
Item 1	Week 6					
	Week 12					
	...					
....	Week 6					
	Week 12					
	...					
Item 58	Week 6					
	Week 12					
	...					
*Control refers to topotecan						
Item 1	Week 6					
	Week 12					
	...					
....	Week 6					
	Week 12					
	...					
Item 58	Week 6					
	Week 12					
	...					

Table 12.8.3 Percentage of patients with an improvement $\geq 10\%$ vs. baseline

Item	Cycle	PM01183		Control*		p-value
		N	%	N	%	
*Control refers to PLD and/or topotecan						
Item 1	Week 6					
	Week 12					
	...					
....	Week 6					
	Week 12					
	...					

[figure not shown]
Item	Cycle	PM01183		Control*		p-value
		N	%	N	%	
Item 58	Week 6					
	Week 12					
	...					
*Control refers to PLD						
Item 1	Week 6					
	Week 12					
	...					
....	Week 6					
	Week 12					
	...					
Item 58	Week 6					
	Week 12					
	...					
*Control refers to topotecan						
Item 1	Week 6					
	Week 12					
	...					
....	Week 6					
	Week 12					
	...					
Item 58	Week 6					
	Week 12					
	...					

Longitudinal analyses will be performed assuming a mixed-effect model with treatment (Y), time effect (days after baseline), and a time-treatment interaction as covariates, using a covariance structure of autoregressive order 1.

Table 12.8.4 Mixed effect model

Item	Estimated point change per day	p-value	Mean change during treatment
*Control refers to PLD and/or topotecan			
Item 1			
....			
Item 58			
*Control refers to PLD			
Item 1			
....			
Item 58			
*Control refers to topotecan			
Item 1			
....			
Item 58			

Figures 12.8.5-12.8.62 Means plot by each item

